## I. Study Synopsis

Study Title	Intracapsular and Intertrochanteric Fracture Fixation with the THP Hip Fracture Plating System Clinical Outcome Study
Abbreviated Study Title	THP Clinical Outcome Study
Sponsor	Zimmer Biomet, Warsaw, Indiana
Protocol Number	CSU2017-22T
Anticipated Start Date	Q3 2018
Study Objectives	
The objective of this observational prospective study is to systematically document the clinical outcome of THP Hip Fracture Plating System when used to treat intracapsular and intertrochanteric fractures.
 
Primary Endpoint:
 
 
Revision rate due to device related complication(s) or non-union of the femur.
 
 
Secondary Endpoints:
 
 
Radiographic and clinical fracture healing of the proximal femur using standard scoring methods.
 

Target Population	190 subjects who have undergone one of the following with the THP Hip Fracture Plating System: 
 
Intracapsular fracture repair (101 subjects)
 
Intertrochanteric fracture repair (89 subjects)
 

Study Design	Multicenter, prospective, observational study
Study Type	Post-Market Clinical Follow-up Study (PMCF)
Sample Size	190
Length of Study	3 years (2 years of enrollment and 1 year of follow-up)
Follow-up Intervals	1 to 6 weeks, 3 months, 6 months, and 12 months after surgery
Inclusion/Exclusion Criteria	
Inclusion Criteria
 
 
Patient must be 18 years of age or older.
 
Patient must be eligible for an open reduction and internal fixation of the proximal femur.
 
Patient must have an intracapsular or intertrochanteric fracture.
 
Patient must have need for alignment, stabilization, and reduction of bone fractures.
 
Patient must have ability and willingness to follow
 

	
postoperative care instructions until healing is complete.
 
 
• Patient must be in good nutritional state.
 
• Patient must be able and willing to sign the IRB/EC approved informed consent.
 
 
Exclusion Criteria
 
 
• Patient is a prisoner.
 
• Patient is a current alcohol or drug abuser.
 
• Patient is known to be pregnant or breastfeeding.
 
• Patient has a psychiatric illness or cognitive deficit that will not allow proper informed consent.
 
• Infection.
 
• Patient conditions including bloody supply limitations, obesity or insufficient quantity or quality of bone.
 
• Patient with mental or neurologic conditions who are unwilling or incapable of following postoperative care instructions.
 
• Patient has foreign body sensitivity. Where material sensitivity is suspected or unknown, testing is to be completed prior to implantation of the device.
 
• Patient is expected to be non-compliant with recommended post-operative weight-bearing instructions.
 

Study Device	THPT™ Hip Fracture Plating System
Outcome Measures	
 
• VAS Pain Scale
 
• EQ-5D-5L
 
• RUSH Score
 
• FIX-IT
 
• Implant Survivorship
 
• Adverse Events
 
• Operative Time
 
• Readmissions
 
• Reoperations
 

Documentation	Electronic Case Report Forms
Statistical Reporting	Data collected will be summarized and reported to each participating investigator. Statistical analysis will be conducted by Zimmer Biomet or its designee.

This protocol is written based on guidelines from ISO 14155 Standard for Clinical Investigation of

Medical Devices For Human Subjects – Good Clinical Practice (i) and is in accordance with US Code of Federal Regulations 21 CFR Parts 11, 50 and 56 (ii)

## II. Data Collection Overview

The following table indicates the necessary case report forms to be completed at the given time point:

Form Name	Enrollment	Operative	Discharge Assessment	1 to 6 Weeks Post-op (+14 days)	3 Months Post-op ( $\pm 30$ days)	6 Months Post-op ( $\pm 60$ days)	1 Year Post-op ( $\pm 90$ days)	Revision
Enrollment Form	X							
Demographic Evaluation	X							
Operative Record		X						
Postoperative Discharge Assessment			X					
VAS Pain				•	•	•	•	
EQ-5D-5L				•	•	•	•	
FIX-IT				X	X	X	X	
X-rays	X	X	X	X	X	X	X	X
Postoperative Follow-up Evaluation				X	X	X	X	
Study Completion		*	*	*	*	*	*	X
**Adverse Event (Complication)	*	*	*	*	*	*	*	X
Protocol Deviation	*	*	*	*	*	*	*	*
Physician Radiographic Assessment (Including RUSH)				*♦	*♦	*♦	*♦	*♦
Explant Device			X	X	X	X	X	X

X Completed by Investigator or Designee (required)
 
 
• Completed by Patient
 
* Completed by Investigator or Designee (as applicable)
 
♦ Independent radiographic review may be performed by Sponsor's designee if requested by the Sponsor.
 
 
** If device related Adverse Event occurs, a Product Experience Report (PER) must be completed and sent to the sponsor as well and include the Operative Report (index and revision) and Radiographs (immediate post-op, all follow-up visits, and pre-revision).
								

## III. Introduction and Purpose

Zimmer Biomet has developed a telescoping lag Screw and Hip Fracture Plate for fixation of fractures of the proximal femur, intracapsular and intertrochanteric femoral fractures. The device will compete with traditional devices, including cannulated screws used for

neck fractures and compression hip screws use for intertrochanteric fractures. Hemi-hip arthroplasty is also an alternative for some patients.

Although various techniques have been developed for internal fixation with open or closed reduction of femoral neck fractures, numerous complications such as non-union and femoral head avascular necrosis may require additional interventions. This study will document the clinical and radiographic outcomes of hip fracture patients, utilizing a hip fracture plate construct manufactured by Zimmer Biomet.

#### **IV. Study Objectives**

The objective of this observational prospective study is to systematically document the clinical outcome of the THP Hip Fracture Plating System when used in fractures of the proximal femur, intracapsular and intertrochanteric fractures, as compared to historical literature data for the same indications when using cannulated or hip screws . These objectives will be assessed using standard scoring systems, radiographic evidence, and adverse event records.

**Safety:** Will be assessed by monitoring the frequency and incidence of adverse events (AE), serious adverse events (SAE), adverse device effects (ADE), serious adverse device effects (SADE), and unanticipated serious adverse device effects (USADE) and device deficiencies.

**Performance:** Will be determined by analyzing the implant survival, overall pain and functional performances on standard scales, subject quality of life, and radiographic parameters of subjects who received the subject device(s). Operative time and readmissions will also be analyzed. Implant survival will be based on removal or intended removal and determined using the Kaplan-Meier method.

- **Overall pain and functional performance** will be based on Visual Analog Scale (VAS) Pain, Rush Score, EuroQol 5D-5L (ED-5D-5L), and Functional Index for Trauma (FIX-IT).
- **Survivorship** will be based on the rate of revision in the study device due to fixation failure or non-union of the femur.
- **Radiographic parameters** to be analyzed may include, but are not limited to, implant fracture, significant implant migration or subsidence, and implant loosening. Other significant findings may also be observed and reported during the course of this study.

It is planned that once sufficient data has been collected allowing meaningful statistical analysis; contributing investigators can use the data for peer reviewed publications, podium presentations and as a basis for surgeon discussions and learning.

**Study Endpoints:** The primary endpoint of this study is defined as the rate of revision after 12 months due to device related complication or non-union of the femur. The secondary endpoints of this study are defined as radiographic and clinical fracture healing of the proximal femur using standard scoring methods.

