3. EQ-5D-5L
4. RUSH
5. FIX-IT
6. X-rays (A/P and lateral views of the hip or pelvis)
7. Physician Radiographic Assessment
8. Adverse Event(s)
9. Protocol Deviation(s)
10. Study Completion
11. Explanted Device

Subjects will be followed post-operatively for 12 months. Unless the study is otherwise closed, data will continue to be collected until the subject completes the study per the protocol, voluntarily withdraws from the study, is withdrawn from the study by the investigator, is lost to follow-up, undergoes revision to remove a study device, (due to complication) including partial removal i.e. screw, or expires. See Management of Incurrent Events for additional details. Reason(s) for study completion must be documented on the Study Completion case report form.

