**D. Management of Incurrent Events**

**1. Failure to Obtain Informed Consent**

Study data will not be collected until the Informed Consent has been

signed and dated by the candidate. If a candidate does not wish to participate (does not sign and date the Informed Consent), data for that candidate will not be collected for this study.

2. Adverse Events

An adverse event is any unfavorable or unintended sign, symptom, or disease that impacts the subject. Adverse event is synonymous with complication or medical event.

See Section IX, Subsection E of this protocol for additional information regarding adverse event classifications. Femur related, serious, and unanticipated events are required to be reported on the **Adverse Event Report** case report form. The completed **Adverse Event Report** case report form must be submitted to the Sponsor in a timely manner. The Investigator or Designee will also promptly provide the Sponsor with any additional requested information required for the Sponsor to comply with regulatory requirements. If applicable per their reporting requirements, the Investigator or Designee will also report applicable adverse event(s) to their IRB or EC.

3. Revision

In the event that removal of one or more of the study related components is necessary (due to complication), the Investigator will determine the best treatment and/or revision method for the subject. Once the revision surgery has been completed, the Investigator or qualified Designee must complete an **Adverse Event Report** case report form as well as a **Study Completion** case report form terminating the subject from the study.

4. Investigator Withdrawal

The Investigator can choose to withdraw a subject from the study if the subject no longer meets study inclusion/exclusion criteria. The reason for the Investigator's withdrawal of the subject must be documented on the **Study Completion** case report form.

5. Subject Withdrawal

Study subjects may choose to withdraw from the study at any time, for any reason. If possible, a final evaluation will be completed for any subject who no longer wishes to participate in the study. The reason for the subject withdrawal must be documented on the **Study Completion** case report form.

6. Lost to Follow-up

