### **A. General Statistical Methods**

Statistical methodology will consist of summarizing collected data descriptively. Categorical data (e.g., gender or race) will be summarized using counts and percentages, and 95% Confidence Interval (CI), over the time periods of interest. Continuous data, such as age, will be summarized by using means, medians, standard deviation, minimum, maximum, and 95% CI over the time periods of interest. Implant survival and return to function will be summarized using a Kaplan-Meier method and presented with rates (as percentages) and confidence intervals.

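### With no rule for competing events, Kaplan-Meier would censor deaths and revised patients in return to function and overstate recovery; the effect on revision is small and runs against the device

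*Combined protocol and SAP*

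**What the plan says.** Section XI.A (General Statistical Methods) names one time-to-event method for two outcomes: "Implant survival and return to function will be summarized using a Kaplan-Meier method and presented with rates (as percentages) and confidence intervals". Section IV (Study Objectives, Performance) gives the event for the first of these: "Implant survival will be based on removal or intended removal and determined using the Kaplan-Meier method". Death is not part of that event. Section IV adds that survivorship "will be based on the rate of revision in the study device due to fixation failure or non-union of the femur". Return to function is mentioned only in XI.A, and its event is not defined.

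Section VIII.I sets the observation period: "Subjects will be followed post-operatively for 12 months". It lists what ends data collection sooner, including when a subject "undergoes revision to remove a study device, (due to complication) including partial removal i.e. screw, or expires". Section IX.D.8 (Study Termination) repeats that list. Section IX.D.3 (Revision) requires, after revision surgery, a Study Completion "case report form terminating the subject from the study".

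The primary endpoint in section IV is "the rate of revision after 12 months due to device related complication or non-union of the femur". No estimator is attached to it. The plan states no censoring rule, no method for competing events and no expected mortality.

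**The concern.** A patient who has died can no longer have the implant removed or regain function. A revised patient leaves the study, so recovery on the study device can no longer be observed. These are competing events. Censoring them in a Kaplan-Meier analysis assumes that such patients kept the same chance of the outcome as those still under observation. One minus Kaplan-Meier then describes a hypothetical population in which nobody dies (or, for function, in which nobody is revised either). It is not the share of enrolled patients who had the outcome, and the plan does not say that it wants the hypothetical quantity.

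The direction differs by outcome. For revision, the reported rate is too high, which counts against the device. For return to function, the reported recovery is too high, which favours it. The revised patients matter most here, because they are the failed fixations and censoring removes them from the recovery figure without counting them as failures. Section XI allows the summaries to support regulatory submissions and publications, so a descriptive recovery percentage should describe the patients who were treated.

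**Working it through.** **Inputs from the plan.** Section XI.B gives assumed revision rates of 15% (intracapsular) and 5% (intertrochanteric), historical rates of about 20% and 7%, a margin of 8% (read here as absolute points), 15% loss to follow-up, and maxima of 101 and 89 subjects.

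**Inputs assumed.** 12-month mortality of 5/10/20/30%, because the plan gives none. 80% return to function by Kaplan-Meier, because the plan gives no rate. Hazards constant over the 12 months.

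**The plan's own figure.** The group sizes fit a one-sample comparison of a proportion with the historical rate plus 8 points:

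n = [z(1−α)·√(pm(1−pm)) + z(power)·√(p1(1−p1))]² / (pm − p1)²

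Alpha and power are not stated; one-sided 5% and 90% are assumed.
- Intracapsular, pm = 0.28 and p1 = 0.15: n = 85, and 85/0.85 = 100 (plan: 101).
- Intertrochanteric, pm = 0.15 and p1 = 0.05: n = 76, and 76/0.85 = 89.4, so 90 (plan: 89).

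Other alpha and power pairs also fit, so these are not uniquely recovered. The sizes do not depend on how deaths are handled.

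**Formula for the gap.** For a 12-month probability p, the hazard is −ln(1−p). Let h be the hazard of the outcome and c the summed hazards of the competing events.
- One minus Kaplan-Meier = 1 − exp(−h)
- Cumulative incidence = h/(h+c) × (1 − exp(−(h+c)))

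The second is never larger than the first.

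**Return to function.** h = −ln(0.20) = 1.609.

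Revision competing, no deaths: c = −ln(0.85) = 0.163. Cumulative incidence = 1.609/1.772 × (1 − exp(−1.772)) = 75.4%, so 80% overstates by 4.6 points.

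| Assumed mortality | Death competing | Overstated by | Death and 15% revision competing | Overstated by |
|---|---|---|---|---|
| 5% | 78.5% | 1.5 | 74.0% | 6.0 |
| 10% | 77.0% | 3.0 | 72.6% | 7.4 |
| 20% | 73.8% | 6.2 | 69.7% | 10.3 |
| 30% | 70.4% | 9.6 | 66.6% | 13.4 |

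The 80% is not critical. With 15% revision and 10% mortality, Kaplan-Meier recovery of 60%, 70% or 90% overstates by 6.3, 7.0 or 7.3 points.

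Timing matters more. With deaths alone, if every death came before any recovery, the true share would be 0.80 × (1 − mortality), which is 72% at 10% mortality. If every death came after the last recovery, there would be no overstatement.

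**Revision, with death competing.**

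| Assumed mortality | Intracapsular, Kaplan-Meier 15% | Overstated by | Intertrochanteric, Kaplan-Meier 5% | Overstated by |
|---|---|---|---|---|
| 5% | 14.6% | 0.4 | 4.9% | 0.1 |
| 10% | 14.3% | 0.7 | 4.8% | 0.2 |
| 20% | 13.5% | 1.5 | 4.5% | 0.5 |
| 30% | 12.7% | 2.3 | 4.2% | 0.8 |

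For scale, 101 × 0.85 = 85.85 and 89 × 0.85 = 75.65 evaluable subjects give binomial standard errors of √(0.15 × 0.85/85.85) = 3.9 points and √(0.05 × 0.95/75.65) = 2.5 points.

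**The case against.** **A reader might infer that the bias reaches the primary comparison and uses up part of the 8-point margin.** The documents do not support that. Kaplan-Meier is attached to implant survival, whose event is removal or intended removal. The primary rate is tied to it only through the wording on survivorship. XI.A also summarises categorical data as percentages with 95% confidence intervals, and the group sizes fit a simple proportion. Even if Kaplan-Meier were used, the shift is below 1 point for intertrochanteric fractures at every mortality tried. For intracapsular fractures it exceeds 1 point only at the 20% and 30% values. It counts against the device, so it could not by itself produce a false claim of non-inferiority. This part of the objection stands.

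**The plan nowhere says that deaths are censored.** This is true. Censoring is inferred from the method, the event definition and the rules that end follow-up. The defect is the missing rule together with what the method does by default.

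**The large figures rest on assumed inputs, for an outcome that is neither a primary nor a secondary endpoint and has no benchmark.** This limits the weight of the point. The mortality range may be too high for this sample: eligibility requires good nutritional state, and section V allows consent after surgery, which can keep early deaths out. But the 4.6-point effect from revision alone needs no deaths and uses the plan's own 15%.

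**Kaplan-Meier is a legitimate measure of device performance, and the historical rates may have used it.** This stands for revision. The plan does not say how the historical figures handled deaths. If they came from Kaplan-Meier, changing only the study's estimator would tilt the comparison towards the device. It does not rescue return to function, where revision is the device's own failure and cannot be treated as uninformative censoring.

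**Conclusion.** The point holds for return to function. Followed as written, the plan would overstate recovery in the device's favour. Starting from an assumed 80% by Kaplan-Meier, the overstatement is 4.6 points from 15% revision alone and 6.0 to 13.4 points with 5% to 30% mortality added. These figures are a sensitivity range under constant hazards, not estimates. They also take the plan's 15% as the rate at which revision ends follow-up. At the 5% intertrochanteric rate, the part due to revision would be smaller.

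For revision, the effect is small (0.4 to 2.3 points intracapsular, 0.1 to 0.8 intertrochanteric) and works against the device. The documents do not support a conclusion that the primary endpoint is biased, or that Kaplan-Meier should be dropped for revision.

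**What to change.** In section XI.A, with matching wording in section IV:

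1. Define the return-to-function event: the instrument, the threshold and the visit or time at which it counts.
2. Estimate return to function by cumulative incidence, with death and revision before recovery as competing events, so that these patients count as not recovered.
3. Report the Aalen-Johansen cumulative incidence of revision at 12 months for each fracture type, with death competing and a 95% confidence interval, alongside Kaplan-Meier.
4. Keep Kaplan-Meier for revision. When comparing with the historical rates, use the estimator that the source used.
5. State which exits are censored (for example, loss to follow-up and withdrawal).
6. Confirm that the Study Completion form captures the date of death. The protocol requires the reason for completion but does not expressly require that date.

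The cost is plan wording and a standard routine. No new data are needed if the date of death is already collected; otherwise one field must be added. The downsides are two revision figures to explain and a less favourable recovery figure.

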## V. Study Design

This is a prospective, multicenter, non-controlled clinical study designed to facilitate the collection and evaluation of pain, function, quality of life, radiographic assessment, and adverse event data. A maximum of 10 sites will contribute to this study to enroll a study maximum of 190 subjects. Enrollment per site will not exceed 57 subjects (30% of the total sample). Each Investigator will be skilled in femur fracture treatment and experienced implanting the devices included in this study, as determined by the Sponsor.

Due to the different historical revision rates for intertrochanteric fractures (~7%) and neck fractures (~20%), study enrollment will be split between the two groups to maintain the integrity of the sample size with an expectant lost to follow-up rate of 15%.

Intertrochanteric fractures will be limited to a maximum of 89 enrolled subjects and intracapsular fractures will be limited to a maximum of 101 enrolled subjects. This will provide enough evaluable data for both indications to show the necessary statistical improvement from the historical revision rates.

Each Principal Investigator will be responsible for obtaining Institutional Review Board (IRB) or Ethics Committee (EC) approval as required prior to conducting the study. In order to avoid potential selection bias, each Investigator will offer study participation to each consecutive eligible patient presenting as a candidate for hip fracture repair using the commercially available (FDA cleared) THP Hip Fracture Plating System. Eligible candidates who express interest in study participation will be offered Informed Consent. All potential study subjects will be required to participate in the Informed Consent process and will not be considered enrolled in the study until the candidate has signed and dated the IRB/EC approved patient Informed Consent. Study data cannot be collected until the candidate has completed the Informed Consent process and signed and dated the IRB or EC approved Informed Consent.

Once Informed Consent has been obtained, preoperative, operative, and discharge documentation will be collected either via retrospective chart review or direct interview with the subject. Patients who have previously received THP Hip Fracture Plating System may be enrolled in the study if Informed Consent occurs prior to the end of the 6 weeks follow-up visit window. This will include retrospective chart review for patients who meet the inclusion criteria (and do not meet any of the exclusion criteria) and have available surgical data. Patients that meet these requirements will be asked to consent to study

participation postoperatively. The consented patients will be followed prospectively at designated follow-up visits if all appropriate IRB/EC approvals and patient consent is obtained. The post-operative clinical and radiographic evaluations will be conducted at 1 to 6 weeks, 3 months, 6 months, and 12 months post-surgery.

Review of radiographs will be completed by the investigators at each clinical follow-up interval to determine radiographic evidence of fracture healing. In addition, the Investigator will review radiographs at each clinical follow-up interval to ensure radiographic evidence of adverse events is documented and reported to the IRB or EC and the Sponsor as required. At the Sponsor's discretion, the Sponsor may request copies of these radiographs for independent radiologic review. The Sponsor may request one central reviewer for all radiographs independent of the surgeon and institution.

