## **G. Baseline/Pre-operative/Operative/Discharge Assessment**

Data collection required for baseline, operative, and discharge will be collected preoperatively if the subject signs their informed consent prior to surgery. If the subject meets all inclusion and none of the exclusion criteria and signs an informed consent prior to the end of the 6 weeks follow-up visit window, retrospective chart review will be conducted for preoperative data. At a minimum, this will include physical exam data, demographic data, and operative data. However, it may include additional information related to pain, function, and radiographic evaluation if available. The following case report forms will be collected baseline, operatively, and at discharge:

1. Enrollment Form
2. Demographic Evaluation
3. Operative Record
4. Postoperative Discharge Assessment
5. X-Rays (any available views)
6. Adverse Event(s)
7. Protocol Deviation(s)
8. Study Completion
9. Explanted Device

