## **K. Radiographic Definitions and Methods**

All postoperative radiographic evaluations performed according to the protocol will be reviewed by the Investigator at the time of the evaluation and documented using the **Physician Radiographic Assessment** case report form. This includes documentation of any significant radiographic findings. In addition, an **Adverse Event** case report form must be completed for those findings indicated by an asterisk on the **Physician Radiographic Assessment** case report form, or for any other findings identified as an adverse event.

[figure not shown]
[figure not shown]
- Non-union definition: A total RUSH score below 18 at six month post-surgery is considered a non-union.

- RUSH scoring examples:

	Cortical Bridging	Cortical Fracture Line Disappearance
Anterior	1	2
Posterior	1	1
Medial	1	1
Lateral	1	1
Total:	4	5

Trabecular Consolidation	1
Trabecular Fracture Line Disappearance	1
RUSH Total:	11

	Cortical Bridging	Cortical Fracture Line Disappearance
Anterior	3	3
Posterior	2	2
Medial	2	2
Lateral	3	3
Total:	10	10

Trabecular Consolidation	3
Trabecular Fracture Line Disappearance	3
RUSH Total:	26

Acceptable views include A/P and lateral views of the hip and/or pelvis and must include view of the implanted devices and the treated fracture and/or healing or healed fracture.

At the Sponsor's discretion, study radiographs may be requested from the sites for independent radiographic review and assessment of appropriate parameters.

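### Consent is allowed up to day 56 after surgery with no reference date for eligibility and no rule for patients already revised, so the 12-month Kaplan-Meier revision rate could read modestly low

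*Combined protocol and SAP*

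**What the plan says.** **Late consent.** Section V (repeated in the note to VI.A) says that patients who have already received the device "may be enrolled in the study if Informed Consent occurs prior to the end of the 6 weeks follow-up visit window". Section VIII.I sets that visit at 1 to 6 weeks with 14 days added. Section VIII.B confirms that retrospectively enrolled subjects may sign after surgery.

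**Endpoint time.** Section IV defines the primary endpoint as revision after 12 months for a device-related complication or non-union. Visits are timed from surgery (VIII.I). Implant survival is summarised by Kaplan-Meier (IV, XI.A), with no entry time for subjects who join after surgery.

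**Eligibility.** For already-implanted patients, Section V requires the criteria to be met and then states: "Patients that meet these requirements will be asked to consent to study" participation. Section VI says the criteria are not to be assessed until the consent form is complete. Infection is exclusion e in VI.B, with no date attached.

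**Safeguard.** "In order to avoid potential selection bias, each Investigator will offer study participation to each consecutive eligible patient" (Section V, repeated in VI and VIII.A).

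**Recording.** On retrospective chart review for preoperative data, VIII.G says: "At a minimum, this will include physical exam data, demographic data, and operative data". The form lists include "9. Explanted Device" (VIII.G) and "11. Explanted Device" (VIII.I), each alongside an Adverse Event form. The table in Section II requires the explant form at discharge and at 1 to 6 weeks, and provides the Adverse Event form from enrollment. Participation ends when a subject "undergoes revision to remove a study device, (due to complication) including partial removal i.e. screw" (VIII.I). Only signers are entered in the log (VIII.C), and no data are collected on people who do not sign (VIII.B, IX.D.1).

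**The concern.** A subject who consents on, say, day 40 contributes 40 days counted from surgery during which the study was not yet observing them. That is harmless if every implanted patient is equally likely to enrol whatever happened in those days. It is not harmless if an early failure makes enrolment less likely.

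The text leaves three ways for that to happen:

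- **Excluded.** If the criteria are applied at consent, as Section VI suggests, a postoperative infection could be read as meeting exclusion e.
- **Not approached.** Participation ends at revision and nothing says that a patient already revised should be enrolled, so a site may think there is nothing left to follow.
- **Declined.** The patient may refuse after a bad outcome.

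In each case the study keeps no record, so the consecutive offer cannot be checked afterwards. The primary endpoint is read against historical rates of about 20% (intracapsular) and 7% (intertrochanteric), so a missed early revision would favour the device.

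**Working it through.** The plan gives no figure for this effect. The check sets out the dates, then a range under stated assumptions.

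**Dates**
- Last day for late consent: 6 × 7 + 14 = day 56.
- Earliest non-union by the plan's definition ("A total RUSH score below 18 at six month post-surgery is considered a non-union"): 182.5 − 60 (visit window) = about day 122. Essentially only revisions for early device-related complications can therefore fall before consent.

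**Inputs from the plan**
- Assumed device revision rates R: 15% intracapsular, 5% intertrochanteric (XI.B).
- Evaluable numbers after 15% loss: 0.85 × 101 = 86 and 0.85 × 89 = 76.

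**Inputs that are assumptions**
- r, the share of subjects consenting after surgery: 50% or 25%.
- g, the share of first-year revisions falling before day 56: 10%, 15.3% (56/365, an even spread) or 30%. The non-union definition argues for the lower values.
- Day of late consent, u: even over days 14 to 56 (mean 35). As a bounding case, everyone at day 56.
- All pre-consent revisions missed or, alternatively, half.

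**Formulas**
- Chance of revision before consent: p = R × g × u/56.
- Rate among late enrollees if all of these are missed: (R − p)/(1 − p). If half are missed, replace p by p/2.
- Reading = (1 − r) × R + r × (that rate averaged over u).

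**Worked example** (R = 15%, r = 50%, g = 30%, u at its mean of 35)
- p = 0.15 × 0.30 × 35/56 = 0.0281
- Late-enrollee rate = (0.15 − 0.0281)/(1 − 0.0281) = 0.1254
- Reading = 0.5 × 0.15 + 0.5 × 0.1254 = 13.8%

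| Case | g = 10% | g = 15.3% | g = 30% |
|---|---|---|---|
| R = 15%, r = 50%, all missed | 14.6% | 14.4% | 13.8% |
| R = 15%, r = 50%, half missed | 14.8% | 14.7% | 14.4% |
| R = 15%, r = 25%, all missed | 14.8% | 14.7% | 14.4% |
| R = 15%, r = 50%, all missed, all late consent at day 56 | 14.4% | 14.0% | 13.0% |
| R = 5%, r = 50%, all missed | 4.9% | 4.8% | 4.6% |

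The documents do not say that late consent starts at day 14. With consent spread over days 0 to 56 (mean 28), the first row becomes about 14.7%, 14.5% and 14.0%.

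**Scale**
- Standard error at 15%: √(0.15 × 0.85/86) = 3.9 points.
- Standard error at 5%: √(0.05 × 0.95/76) = 2.5 points.

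**Crude proportion** (simulated; n = 101, 15% lost, r = 50%, R = 15%; events over events plus completers). This estimator starts too high, because subjects lost without an event leave the denominator.
- All pre-consent revisions enrolled: 16.1% (g = 15.3%) or 16.3% (g = 30%).
- All missed: 15.4% or 14.9%.

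It moves down, but ends above or close to the true 15%.

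**Delayed-entry Kaplan-Meier** (same simulation)
- All missed, r = 50%: ordinary 14.3% and delayed-entry 14.9% (g = 15.3%); 13.8% and 15.0% (g = 30%).
- All enrolled, r = 100%: ordinary 15.0% at both values of g; delayed-entry 14.5% and 13.9%.

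Delayed entry repairs the estimate when early failures are missed, and damages it when they are captured and few or no subjects consent before surgery.

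**The case against.** The best defence is that the plan already captures early revisions. Section II requires the explant form at discharge and at 1 to 6 weeks. The Adverse Event form runs from enrollment, IX.D.2 requires femur-related and serious events to be reported, and the late-consent limit is the end of that same visit window. The chart-review minimum in VIII.G describes preoperative and operative data, not everything collected on a late enrollee. The rule ending participation at revision governs people already enrolled and itself generates an Adverse Event report (IX.D.3). This stands: a reader might infer that revisions between discharge and consent go unrecorded in late enrollees, and the documents do not support that. The gap concerns patients who never enrol.

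No section excludes a revised patient, and the offer must be consecutive. That stands too: the loss is possible, not shown. The downward direction is also an assumption. Patients with complications might be seen and approached more often, and deaths before consent could offset the bias slightly.

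The infection route can be called strained, since several criteria describe status before implantation. That is a fair reading, but nothing in the text fixes it, and Section VI points to consent.

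A reader might also infer that the bias could supply the device's whole assumed advantage. Making a true 20% read 15% would require about 29% of all revisions to be missed: 0.20 × 0.71/(1 − 0.20 × 0.29) = 15.1%. With r = 50%, g = 30% and consent spread over days 14 to 56, the share missed is 0.5 × 0.30 × 35/56 = 9.4%. Nothing in the documents supports the larger figure.

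**Conclusion.** The point holds as a minor one. Late consent to day 56, endpoint time from surgery without an entry rule, and an undated and inconsistently sequenced eligibility check together leave room for early failures to stay out of the study unrecorded. If revised patients are less likely to enrol, the Kaplan-Meier rate is biased low.

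The size cannot be determined from the documents, which give neither the share consenting late nor the timing of revisions. It is probably modest: 0.4 to 1.2 points at a true 15% if half consent late and all pre-consent revisions are missed, and 2.0 points in the most extreme bounding case shown. All are below one standard error. The bias is zero if nobody consents after surgery or if all early failures are enrolled.

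It would go too far to say that any estimate of the rate must fall below the truth. The crude proportion shifts down but need not do so.

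**What to change.** 1. **Eligibility (V, VI).** Reconcile the two sections on whether the criteria are judged before or after consent. State that eligibility of postoperatively consented subjects is judged on status at the date of surgery, so that a later infection or revision does not exclude them.
2. **Enrolment and counting (V, VIII.G, XI.A).** State that patients revised before consent are offered enrolment, that revisions are counted from surgery, and that a late enrollee's chart review covers the whole interval from surgery to consent.
3. **Reporting (XI.A).** Report the revision rate separately for subjects consented before and after surgery, using the consent dates already recorded. State possible missed pre-consent revisions as a limitation.
4. **Optional.** Add a Kaplan-Meier analysis with delayed entry at the consent date as a sensitivity analysis only. State that it assumes consent timing is unrelated to revision risk and is unreliable if few subjects consent before surgery. The ordinary estimate from surgery stays the main one.

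The cost is a short amendment (with IRB/EC approval where required), a slightly longer chart review for late enrollees, and subgroup estimates that will be imprecise in cohorts of 101 and 89.
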